### **1.2. Background**

AD can have detrimental impacts on overall quality of life for both patients and their families. PROs provide an efficient way to monitor the impact of disease and effect of treatment(s) on patients' physical, mental, and social health. Additionally, PROs can elucidate the impact of the disease on caregivers and families. Topical corticosteroids have been recommended as the first line treatment for AD, but their chronic use is associated with adverse effects, including dyspigmentation, telangiectasias, acne, and skin atrophy (5). Crisaborole (Eucrisa™) is a recently approved nonsteroidal topical ointment for the treatment of patients ( $\geq 2$  yrs of age) with mild to moderate AD. Crisaborole has a novel mechanism of action by inhibiting the phosphodiesterase-4 enzyme which has been shown to be elevated in AD leukocytes and is thought to be responsible for the tissue inflammation observed in this disease. Like tacrolimus, which has a different mechanism of action (e.g. calcineurin antagonist), it provides a safer alternative to topical steroids, which is especially relevant for children with AD. Unfortunately, it can be difficult to obtain prior authorization for this new medication. In contrast, tacrolimus 0.03% ointment is now available as a generic and is therefore much easier to prescribe because more insurance companies cover it for children (2-15yrs of age) with moderate AD. Many clinicians believe crisaborole to be more effective than tacrolimus; however long-term comparator studies have not been done. Paller *et al* showed that crisaborole was better than vehicle in children and adults with AD; however no baseline secondary measures (e.g., pruritus, signs of AD) were reported (5, 6). Nevertheless, recent post-hoc analysis of Phase 3 crisaborole studies observed a very early reduction in itch that may have a significant effect on patient and caregiver PROs (7) providing a potential advantage for crisaborole. This study will use a series of PROs to monitor the treatment effects of crisaborole and tacrolimus 0.03% over a 12 week period of time. The treatment for a chronic inflammatory disease characterized by flares and remissions must be longer than 30 days (i.e., 1 month) (5). We anticipate that crisaborole will

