### 3.5. Inclusion Criteria:

#### Pediatric Subjects:

- a) Male and female subjects of inclusive ages of 2 to 15 years at screening visit.

- b) Diagnosis of  $\leq$ moderate atopic dermatitis or eczema (ISGA 2 or 3 and  $\geq 3\%$  BSA, excluding scalp).
- c) If subject is taking or prescribed antihistamines, subject must be on stable dose of antihistamines.
- d) If subject is taking topical steroids, subject must be on stable dose of topical steroid.
- e) Subjects currently taking tacrolimus (i.e., Protopic), crisaborole (i.e., Eucrisa), or other topical steroid-sparring medications are eligible for this study if he/she agrees to a two week “washout period” prior to starting study procedures (See “washout period” described below on page 9).
- f) If subject is taking systemic anti-inflammatory therapy (i.e., cyclosporine, etc), subject must be on a stable dose of the systemic anti-inflammatory medication for at least six week prior to enrollment and it must be anticipated that this dose would not change during their participation in this study, unless deemed medically necessary. Any changes in medication dose due to flaring of atopic dermatitis or side effects will be documented on the *AD Flare Medication Form* and *AE Source Doc* (see page 19).
- g) Caregiver (i.e., adult parent or guardian) must agree to participate in the study with the patient.
- h) Subject must be able to read and speak English.
- i) Subject, ages  $\geq 8$  years, is able to give assent.

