**4. SUBJECT IDENTIFICATION, RECRUITMENT, AND CONSENT**

**4.1. Subject Identification & Recruitment**

The Dermatology Clinical Trials Unit (CTU) will identify eligible subjects through electronic medical record for patients between the ages of 2 to 15 years with diagnosis of atopic dermatitis and/or eczema in [REDACTED]. The treating Dermatologist (i.e., [REDACTED])

[REDACTED], or the CTU MD fellow will determine if patient has mild to moderate atopic dermatitis (ISGA 2 or 3) and 3% BSA can be enrolled in the study.

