## 5. METHODS AND PROCEDURES

### 5.1. Study Procedures

- Study personnel will complete the electronic **Screening Log** to monitor all subjects approached for participation in this study, the outcome of the assent/consent process (declined or enrolled), and reason for declining participation.
- Study Personnel will complete the **Eligibility Checklist** for each pair of subjects who provide assent and consent for participation in this study.
- **Washout Period:** Patients who are already taking tacrolimus (i.e., Protopic), crisaborole (i.e., Eucrisa), or any steroid- sparring medication for atopic dermatitis are eligible for the study if he/she agrees to discontinuation of the medication for two weeks (i.e., 14 days) prior to starting study procedures. If the patient agrees to the two week "washout period", assent and informed consent can be obtained during that clinic visit. A study visit will be scheduled for the patient and caregiver at a convenient time at least two weeks (i.e., 14

days) from the day of assent/consent. After the two week “washout period”, the subject will return to clinic for the baseline study visit and be randomized to tacrolimus 0.03% or crisaborole. The subject will either be given a tube of tacrolimus 0.03% or crisaborole. All study procedures will continue as described below starting with the **ASPIRE On-study Form**.

- Assent and informed consent are obtained from each subject, without coercion, prior start of any study procedures. Assent Form 1 will be used for subjects ages 8 to 12 years and Assent Form 2 will be used for subjects ages 13 to 15 years. Informed consent will be completed by the parent/adult caregiver. The caregiver subject will provide their name, mailing address, and signature on the **Study Reimbursement Form**. Each subject (child and adult) will complete a W9 form for study reimbursement.
- Study personnel will notify the caregiver that they will be contacted by phone for reminders about upcoming study appointments and screening for any adverse reactions. Study personnel will ask if leaving a voicemail message is okay in case a call is missed. This information will be kept in a password-protected excel file **Call Log** located in the study folder on the Dermatology CTU’s University sharedrive. Study personnel will only have access to this study folder and the excel file.

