*Comprehensive Study Log:* This is a password-protected excel spreadsheet that contains a log for all subjects in the study. The information kept in this file include: Subject Pair ID, Caregiver Name, AD Patient Name, AD Patient MRN, Screened & Eligible, Assent Completed, Consent Completed, Screen Fail, Baseline Complete, 6 Week Complete, 12 Week Complete, Completed Study, Withdrawal, Loss to Follow-up, and Topical Treatment. Study personnel will complete the required subject information and check the appropriate boxes as the study progresses to monitor subject participation in the study.

*ASPIRE On-Study Form:* This form captures demographic information on both the caregiver and patient subjects, as well as relevant clinical information for the patient subjects. This form will be completed electronically and submit information directly to the secure REDCap database at the University of Rochester Medical Center. This form will collect the following:

- Subject Pair ID
- On Study Date
- Washout Period Required (yes/no)
- Caregiver Initials
- Relation of Caregiver
- Caregiver Gender
- Caregiver Age
- Caregiver Race
- Caregiver Ethnicity
- AD Patient Initials
- AD Patient Gender
- AD Patient Race
- AD Patient Ethnicity
- AD Patient Medical History
- AD Patient Current/Previous Treatments for AD
- AD Patient All Current Medications

Assessment Forms: These forms capture the EASI score, ISGA score, %BSA score, and topical treatment tube weight at each assessment (Baseline, 6 Week Assessment, and 12 Week Assessment). These forms will be completed electronically in REDCap during each specified assessment.

Withdrawal Form: This electronic form (REDCap) will be used to document the time and reasons for withdrawals during the study. This form will electronically capture withdrawal information for the study and submit the information directly to a secure REDCap database at the University of Rochester Medical Center.

AD Flare Medication Form: This electronic form (REDCap) will be used to document any extra medication prescribed to control an atopic dermatitis flare in a study subject. Study personnel will record the name of medication, dosage, date started, date ended, and continued for remainder of study (yes/no) for the extra medication. Subjects will remain on study unless he/she has is prescribed systemic anti-inflammatory therapy for atopic dermatitis. The treating dermatologist will manage and monitor the flare at their discretion.

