#### **5.4. Randomization**

Randomization will assign a pediatric subject to one of two topical treatments (crisaborole or tacrolimus 0.03%) at a ratio of 1:1. Randomization will use a computerized pseudorandom number generator and will employ a random block size of 4 or 6. Study personnel will obtain randomization assignment in REDCap.

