### 13. SCHEDULE OF EVENTS AND DATA COLLECTION

Study Procedures	Screening	Baseline Assessment	3 Week	6 Week Assessment	9 Week	12 Week Assessment
Eligibility Checklist 	X	X				
Assent and Informed Consent 	X	X				

Randomization	X	X					
Screening Log		X					
Comprehensive Study Log	Completed as needed throughout the study.						
Reimbursement Form/W9	X	X					
ASPIRE On-Study Log	X	X					
Drug Accountability Record		X					
Assessment Form:							
ISGA		X		X		X	
EASI		X		X		X	
%BSA		X		X		X	
AD Patient PROs:							
PROMIS Itch		X		X		X	
PROMIS Pain Interference		X		X		X	
PROMIS Anxiety		X		X		X	
PROMIS Depression		X		X		X	
CDLQI		X		X		X	
CSHQ		X		X		X	
Caregiver PROs:							
CBI		X		X		X	
FDLQI		X		X		X	
AD Flare Medication Form		Completed as necessary during study.					
AE Monitoring			X	X	X	X	
Call Log			X	X	X	X	
AE Source Doc	Completed as necessary during study.						
Pfizer SAE Form/Cover Sheet	Completed as necessary during study.						
Withdrawal Form	Completed as necessary during study.						
Pediatric Subject							
Reimbursement Form/\$10 Gift Card		X 		X 		X 	
Request For Payment (RFP) for Caregiver Reimbursement		Completed at completion of study procedures and/or subject participation					

Eligibility checklist can be completed before or at the Baseline Assessment.

Assent and consent can be obtained prior to Baseline Assessment.

Completed after assent and consent are obtained and can be same visit as assent and consent.

Pediatric subject reimbursed with gift card at completion of study visit. Subjects must complete and sign the Pediatric Reimbursement Form at each visit to receive the \$10 gift card

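### Current users of either trial ointment can be randomised back to it after a 14-day washout; this may tilt the arm comparison, in a direction and by an amount the plan cannot show

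*Combined protocol and SAP*

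**What the plan says.** **Entry.** Section 3.5 criterion b requires "moderate atopic dermatitis or eczema (ISGA 2 or 3 and" at least 3% BSA, and names no time point. Criterion e adds: "Subjects currently taking tacrolimus (i.e., Protopic), crisaborole (i.e., Eucrisa), or other topical steroid-sparring medications are eligible for this study if he/she agrees" to two weeks off the drug. It sets no limit on the number of such children, their duration of use or their earlier response. Section 3.6 has no exclusion for previous inadequate response.

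**Allocation.** After the washout, section 5.1 has it that "the subject will return to clinic for the baseline study visit and be randomized to tacrolimus 0.03% or crisaborole", so a child may be assigned the ointment just stopped. Section 5.4 "will employ a random block size of 4 or 6" and names no stratification factor.

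**Timing of the severity check.** In section 4.1 the treating dermatologist or the fellow "will determine if patient has mild to moderate atopic dermatitis (ISGA 2 or 3) and 3% BSA can be enrolled in the study". Footnote 1 of section 13 reads: "Eligibility checklist can be completed before or at the Baseline Assessment".

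**Access to the two drugs.** Section 1.2 says that crisaborole authorisation can be hard to get, whereas "tacrolimus 0.03% ointment is now available as a generic and is therefore much easier to prescribe because more insurance companies cover it".

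**Data and analysis.** The ASPIRE On-Study Form (section 5.3) records "Washout Period Required (yes/no") and the child's current and previous AD treatments. Section 11.2 compares the arms on itch and pain by t-test. It lists no covariates for its ANCOVA and plans nothing by prior use.

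**Aim.** Section 2.1 expects the trial to show whether crisaborole is the better overall treatment for children with AD.

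**The concern.** If severity is judged while the child is still on the ointment, a current user enters only with ISGA 2 or 3 disease despite treatment; a user who is clear or almost clear does not enter. Such children are partly selected for incomplete response to that drug. Randomisation balances their number between arms in expectation. It does not cancel the effect of the selection, because the poorer response is expected only in the arm that gives the same drug again. If most of them came from tacrolimus, the tacrolimus arm would look worse than it would in children new to both drugs.

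That is the direction the sponsor hypothesises, and section 2.1 frames the result as an answer for children with AD generally. A crisaborole advantage could then partly reflect who was admitted, and no planned analysis would show this.

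**Working it through.** **Step 1: when is severity judged?** The sections do not agree on one time point.

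| Source | When | State of a washout child |
|---|---|---|
| 4.1 | At identification in clinic | On drug |
| 5.1 | Consent may be taken at that clinic visit; washout follows; ISGA, EASI and %BSA at baseline | At least 14 days off drug at baseline |
| 13, table | ISGA, EASI and %BSA first scheduled at baseline | Off drug |
| 13, footnote 1 | Checklist before or at baseline | Either |

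Judged on drug, the rule favours incomplete responders. Judged off drug, a child well controlled on tacrolimus who flares after stopping can qualify, so the rule can favour responders and the tilt can reverse.

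**Step 2: size of the tilt.** No figure for this is in the documents. Assumed inputs:
- f: share of enrolled children who are prior users of a trial ointment (0.1 to 0.5)
- s: share of those whose drug was tacrolimus (0.5 to 1)
- L: PROMIS points of response lost when re-assigned the same drug (2 to 7 if selected on drug; negative if selected as responders)

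The shortfall is f·s·L in the tacrolimus arm and f·(1−s)·L in the crisaborole arm, so the tilt towards crisaborole is f·L·(2s−1).

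**Step 3: effect on the test.** Section 11.1 gives 20 evaluable pairs per arm and SD 10, taken here as the SD of change. The standard error of the arm difference is 10·√(2/20) = 3.16. With a true difference of zero and a two-sided 0.05 t-test on 38 degrees of freedom (noncentral t):

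| f | L | s | Tilt (points) | Tilt/SE | Two-sided rejection | Significant for crisaborole (nominal 2.5%) |
|---|---|---|---|---|---|---|
| 0.1 | 2 | 1 | 0.2 | 0.06 | 5.0% | 2.9% |
| 0.3 | 5 | 0.5 | 0 | 0 | 5.0% | 2.5% |
| 0.3 | 5 | 0.75 | 0.75 | 0.24 | 5.6% | 4.2% |
| 0.3 | 5 | 1 | 1.5 | 0.47 | 7.5% | 6.7% |
| 0.5 | 5 | 1 | 2.5 | 0.79 | 12.0% | 11.7% |
| 0.5 | 7 | 1 | 3.5 | 1.11 | 19.0% | 18.9% |

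Negative L gives the same figures in favour of tacrolimus.

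**Step 4: chance imbalance, a separate matter.** Assume 12 prior users among 40 children, split 20/20 at random, ignoring blocking. The hypergeometric chance of an 8:4 or worse split in either direction is 2 × (0.1092 + 0.0343 + 0.0063 + 0.0006) = 0.30. Stratification removes this. It leaves the tilt in step 2 unchanged.

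**Step 5: precision of an analysis without prior users.** The 95% half-width is t × 10·√(2/n):
- 20 per arm: 2.024 × 3.16 = 6.4 points
- 14 per arm (f = 0.3): 2.056 × 3.78 = 7.8 points
- 10 per arm (f = 0.5): 2.101 × 4.47 = 9.4 points

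The real numbers will be lower, since children under 5 complete no itch or pain measure (section 5.1).

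**The case against.** The strongest reply is that randomisation gives a valid comparison among the children enrolled. That stands: this is not confounding between arms. The concern is about carrying the result over to children with AD generally, which section 2.1 invites.

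A reader might infer that the protocol itself expects prior users to be mostly tacrolimus users. It does not say so. Section 1.2 speaks only of ease of prescribing and gives no share. Criterion e also covers other steroid-sparing topicals, so the washout group is wider than the two trial drugs.

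A reader might also conclude that the comparison is biased towards crisaborole. The documents do not support that, for three reasons. The timing of the severity check is open, and judging it after washout could select tacrolimus responders. Current use is not proof of failure, since adherence and duration are not entry conditions. And baseline follows withdrawal, so a child put back on tacrolimus may gain from resuming it, which would offset an assumed shortfall.

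Finally, the information is not lost: the On-Study Form holds it. What is missing is a plan to use it. None of these replies supplies one.

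**Conclusion.** The gap is real. Children with active disease on a trial ointment can be admitted and re-assigned to it, and eligibility, randomisation and analysis all leave this unaddressed. The comparison may be tilted towards crisaborole as an answer for children with AD generally. Direction and size are unknown.

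The illustrated 0 to 3.5 points rests wholly on assumed f, s and L. It favours crisaborole only if tacrolimus predominates among prior users (s above 0.5) and prior use signals a poorer response (L above 0). With f = 0.3 and L = 5, the tilt is 0.75 to 1.5 points for s of 0.75 to 1. That is about a quarter to a half of one standard error, and below the 5-point change the protocol treats as clinically important.

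This justifies a specified check and a clear timing rule. It does not justify calling the comparison biased, nor does it by itself require current users to be excluded.

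**What to change.** 1. **Section 11.2.** Pre-specify a sensitivity analysis of the between-arm comparison of itch and pain that leaves out children with current or previous use of either trial ointment. Define the group from the treatment history on the On-Study Form. The washout flag alone will not do: it also covers other steroid-sparing topicals, and it misses children who stopped a trial ointment earlier. Report whether any superiority statement is consistent with this analysis.
2. **Section 5.4.** Stratify the REDCap randomisation by prior use of either trial ointment (yes/no), and include that factor in the ANCOVA, applied to the arm comparison. State that this handles chance imbalance only.
3. **Sections 4.1, 5.1 and 13.** Reconcile when qualifying ISGA and BSA are judged for washout children, and record for each child whether it was on or off drug. Which time point to use is for the sponsor to decide.

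**Cost.** One stratification factor, one extra analysis on data already collected, and one clarified and recorded time point. Treatment history must be taken before randomisation. The restricted analysis is smaller, with a half-width of roughly 8 to 9 points in the cases above. It cannot confirm or rule out a tilt of one or two points, so it is supportive only.

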#### **Caregiver Subjects:**

- a) Subject must be at least 18 years old and the parent or guardian of the eligible pediatric subject.
- b) Subject must be able to read and speak English.
- c) Subject must be able to give informed consent.

#### **3.6. Exclusion Criteria**

- a) Pediatric subjects  $<2$  years old or  $>15$  years old *are not* eligible for participation in this study.
- b) Pediatric subjects with a diagnosis with another skin disease (i.e., not atopic dermatitis or eczema) are excluded to prevent confounding of results.
- c) Caregiver subject  $<18$  years old are excluded.
- d) Pediatric subject participation without caregiver participation is not allowed.

#### **3.7. Women & Children**

This study will enroll both women (18 year or older) and children (ages 2 to 15 years, inclusive).

#### **3.8. Targeted Enrollment**

Estimated enrollment for gender, race, and ethnicity for the study is shown below:

#### **Pediatric Subject (2 to 15 years):**

Racial Categories	Ethnic Categories				Total	
	Not Hispanic or Latino		Hispanic or Latino			
	Female	Male	Female	Male		
American Indian/Alaska Native	0	0	0	0	0	
Asian	1	1	0	0	2	
Native Hawaiian or Other Pacific Islander	0	0	0	0	0	
Black or African American	7	4	0	0	11	
White	19	14	1	0	34	
More Than One Race	1	0	0	0	1	
Total	28	19	1	0	48	

**Caregiver Subjects ( $\geq 18$  years):**

Racial Categories	Ethnic Categories				Total	
	Not Hispanic or Latino		Hispanic or Latino			
	Female	Male	Female	Male		
American Indian/Alaska Native	0	0	0	0	0	
Asian	3	0	0	0	3	
Native Hawaiian or Other Pacific Islander	0	0	0	0	0	
Black or African American	8	3	0	0	11	
White	27	5	1	0	33	
More Than One Race	1	0	0	0	1	
Total	39	8	1	0	48	

**4. SUBJECT IDENTIFICATION, RECRUITMENT, AND CONSENT**

**4.1. Subject Identification & Recruitment**

The Dermatology Clinical Trials Unit (CTU) will identify eligible subjects through electronic medical record for patients between the ages of 2 to 15 years with diagnosis of atopic dermatitis and/or eczema in [REDACTED]. The treating Dermatologist (i.e., [REDACTED])

[REDACTED], or the CTU MD fellow will determine if patient has mild to moderate atopic dermatitis (ISGA 2 or 3) and 3% BSA can be enrolled in the study.

**4.2. Informed Consent Process**

Study personnel and/or dermatologist will identify eligible subjects. Eligible subjects will first be asked if they wish to hear about a potential clinical trial for atopic dermatitis. If the subject expresses interest in the study, the study personnel will approach the subject to discuss the study and obtain informed consent/assent from the patient and caregiver.

All study materials are in English, therefore all subjects must be able to read, speak, and understand English. Current FDA, ICH, NCI, state, federal, and institutional regulations concerning informed consent will be followed. Verbal assent will be obtained from pediatric subjects using the study Verbal Assent Script. Study personnel will read the verbal assent script to the pediatric subject and parent, answer all questions, and complete the form if the subject wishes to participate. All pediatric subjects (ages 8 to 12 years) must provide assent using Assent Form 1 and have their parent (i.e., adult caregiver) provide consent for participation in this study. All pediatric subjects (ages 13 to 15 years) must provide assent using Assent Form 2 and have their parent (i.e., adult caregiver) provide consent for participation in this study. Assent is not required for pediatric subjects less than 8 years old; however parent consent and permissions is required. Study personnel will discuss the informed consent form with the adult caregiver subjects (i.e., parent or guardian). The informed consent for will be a dual consent form on which the adult subject consents to participation as a caregiver in the study and also consents to their child's participation in the study. Additionally, during the consent process both subjects will be asked to complete a W9 form for reimbursement purposes. The adult subject will provide their name, mailing address, and signature on the Study Reimbursement Form to ensure that reimbursement can be mailed to him/her after study participation has completed.

The consent and assent process will be free of coercion and undue influence. Study personnel will then explain the project to the potential subjects and answer all questions. The subject will be provided sufficient information and time make a thoughtful and rational decision on participation. The subject will be given the opportunity to take the consent form home for review and discussion with family members before finalizing his/her decision. After the assent form and informed consent forms are signed, subjects will be given a copy of the document, along with the phone numbers of the study personnel to call if they have further questions. The completed assent and consent forms will be kept in the subject's study folder and stored in a locked office in a locked cabinet.

